6.5.1. Neutralizing antibody titers and antibody titers (ELISA)

Definition

For each subject and each time point two titers for each variant will be determined, as each sample will be measured in replicate. The response per subject and timepoint is defined as the geometric mean of the two titers.

Analysis

Antibody titers (ELISA) derived from reference will be summarized using descriptive statistics for all time points for Group A, Group B and the immunology subset. Additionally, GMT with 95% CI will be presented.

The same analysis will be performed for antibody titers (ELISA) derived from SARS-CoV-2 variant B.1.351 for Group A only.

The antibody response will be listed.

Figures: For each vaccine type, antibody titers (ELISA) will be presented graphically displaying GMT with 95% CI at all time points (two line plots, one with linear and one with log scaled y-axis). For group A, additionally, the same plot will be created by treatment group.

The same analysis will be repeated for neutralizing antibody titers.

6.5.2. Neutralizing antibody titers and antibody titers (ELISA) fold rise

Definition

The fold rise of the antibody response will be calculated for all post-baseline time points as post-dose value divided by baseline value. The baseline value will be the BNT162-14 baseline, i.e., the last value prior (predose V1) to first injection of IMP (Dose 1) given in this BNT162-14 trial on Day 1, including unscheduled visits.

Analysis

The fold rise in antibody titers (ELISA) derived from reference will be summarized using descriptive statistics for all time points for Group A, Group B and the immunology subset. Additionally, GMFR with 95% CI will be presented.

The same analysis will be performed for antibody titers (ELISA) derived from SARS-CoV-2 variant B.1.351 for Group A only.

Antibody titers (ELISA) fold rise will be listed.

Figures: The fold rise of antibody titers (ELISA) will be presented graphically displaying GMFR with 95% CI at all time points (line plot).

The same analysis will be repeated for neutralizing antibody titers

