8.10.1 Neutralizing antibody titers and antibody binding (NATAB)

Neutralizing antibody titers and antibody binding assessment comprise of:

- A functional antibody titer, e.g., VNT or an equivalent assay (e.g., pVNT assay).
 - Seronegative is defined as titers below the starting dilution (i.e., below the limit of detection of the assay).
- Seroconversion after immunization is defined as a 4-fold increase in titer.
 - o for seronegative pre-immunization sera: a titer ≥ 4-times the limit of detection.
 - for seropositive pre-immunization sera: a titer which is 4-fold higher than the measured pre-immunization titer.
- An antibody binding assay, e.g., ELISA or an equivalent assay.
 - Seroconversion after immunization is defined as a 4-fold increase in titer/antibody concentration.

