9.4.1 General considerations

In general, data will be summarized by groups (i.e., two randomized subgroups in Group A and non-randomized Group B with an immunology subset). Data may be pooled with trials BNT162-01 and BNT162-04.

Continuous variables will be summarized by group using the following descriptive statistics: number of subjects (n), mean, standard deviation, median, minimum, and maximum.

Categorical variables will be summarized by group presenting absolute and relative frequencies (n and %) of subjects in each category.

Baseline is defined as last available value prior to first dose of IMP.

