1.1. Objectives and endpoints

Table 2: Objectives and endpoints

Objectives	Endpoints
Primary	
To determine the safety and tolerability of one or two boosting doses of Comirnaty or one dose of BNT162b2s01 in BNT162- 01 trial subjects, or two boosting doses of Comirnaty in BNT162-04 trial subjects.	 For all Group A and Group B subjects: The proportion of subjects in each treatment group with at least one SAE or the proportion of AESIs occurring up to 26 weeks after the first IMP injection. For Group A and a selected subset of Group B subjects: The frequency of solicited local reactions (pain, tenderness, erythema/redness, induration/swelling) at the injection site recorded up to 7 days after each IMP injection. The frequency of solicited systemic reactions (vomiting, diarrhea, headache, fatigue/tiredness, fever, chills, nausea, new or worsened muscle pain, new or worsening joint pain) recorded up to 7 days after each IMP injection. The proportion of subjects with at least one unsolicited TEAE occurring up to 28 days after IMP injection in each treatment group.

Objectives	Endpoints
Secondary	
To describe changes in SARS-CoV-2 neutralizing antibody titers from baseline to reference and SARS-CoV-2 variant B.1.351.	 For Group A and Group B subjects (except transplant subjects): Antibody titers to recombinant S1 and RBD protein derived from reference and SARS-CoV-2 variant B.1.351** will be assessed at baseline (Day 1) and then Day 8, Weeks 3*, 4, 7*, 12, and 26: Neutralizing antibody titers. Antibody titers (ELISA). SARS-CoV-2 functional cross-neutralization of variant B.1.351** to reference strain.
	 * Group B only ** Group A only For Group B transplant subjects only: Antibody titers to recombinant S1 and RBD protein derived from SARS-CoV-2 will be assessed at baseline (Day 1) and then Day 8, Weeks 4, 12, and 26 post Dose 1, and at Dose 2 (Day 1) and then Day 8, Weeks 4, 12 and, 26 post Dose 2: Neutralizing antibody titers Antibody titers (ELISA)
Exploratory	

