6.1.1. Tables and listings

Tables

In general, data will be summarized as follows:

- Group A by vaccine [Comirnaty[®], BNT162b2s01], and total
- Group A subjects having received Comirnaty[®] by HIV infection status
- Group A subjects having received BNT162b2s01 by HIV infection status
- Group B by transplant status, and total
- Group B immunology subset by transplant status, and total

Descriptive summary tables and figures will be based on scheduled visits.

Continuous variables will be summarized using the following descriptive statistics: number of subjects with non-missing data (n), mean, standard deviation (SD), median, minimum (min) and maximum (max).

Descriptive statistics of titer and fold rise of titer will additionally include geometric mean and its two-sided 95% confidence interval (CI). The geometric mean titer (GMT) is calculated as the mean of the logarithm of the functional antibody titers, backtransformed into the original scale. Two-sided CIs will be obtained by calculating CIs using t-distribution for the mean of the logarithmically transformed assay results and transforming the limits back to the original scale.

Geometric mean fold rise (GMFR) is calculated as the mean of the difference of logarithmically transformed assay results (post vaccination time point – pre vaccination time point) and back-transformed into the original scale. Two-sided CIs will be obtained by calculating CIs using Student's t-distribution for the mean difference of the

logarithmically transformed assay results and transforming the limits back to the original scale.

Categorical variables will be summarized presenting absolute and relative frequencies (n and %) of subjects in each category (including the category 'missing' if applicable). Percentages will be calculated based on the number of subjects in the respective analysis set (N) as denominator if not stated differently. Percentages may be presented with exact 95% Clopper-Pearson CIs.

SDs and CIs will only be calculated if values from at least 3 subjects are available.

Listings

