6.5.3. Seroconversion

Definition

Seroconversion is defined as a minimum of 4-fold rise of antibody titers as compared to

- parent trial (BNT162-01 or BNT162-04) baseline (only for titers derived from reference strain;baseline refers to pre-dose V1 in BNT162-01 or pre-dose V1 in BNT162-04)
- BNT162-14 baseline, i.e., the last value prior to first injection of IMP (Dose 1) given in this BNT162-14 trial on Day 1, including unscheduled visits (for both titers derived from reference strain and from SARS-CoV-2 variant B.1.351)

Analysis

The number of subjects with seroconversion in antibody titers (ELISA) derived from reference will be summarized by number and percentage with 95% confidence interval for all post-baseline time points for Group A, Group B and the immunology subset. The denominator of the percentages will be the number of subjects with data available at the respective visit.

The analysis based on BNT162-14 baseline, will be performed for antibody titers (ELISA) derived from SARS-CoV-2 variant B.1.351 for Group A only.

Seroconversion data of the antibody titer (ELISA) will be listed.

The same analysis will be repeated for neutralizing antibody titers

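### For transplant subjects the SAP refers every post-Dose-2 fold rise and seroconversion to a pre-Dose-1 value, so no planned table shows what Dose 2 itself did within a subject; separately, the stated blood volume and trial duration leave out Table 2a

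*SAP*

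**What the plan says.** - **Fold rise, SAP 6.5.2.** Each post-baseline titer is divided by one reference: "The baseline value will be the BNT162-14 baseline, i.e., the last value prior (predose V1) to first injection of IMP (Dose 1".
- **Seroconversion, SAP 6.5.3.** This is a rise of at least 4-fold over the parent-trial baseline (reference strain only) or over the "BNT162-14 baseline, i.e., the last value prior to first injection of IMP (Dose 1) given in this BNT162-14 trial on Day 1". For the percentages, the "denominator of the percentages will be the number of subjects with data available at the respective visit".
- **Baseline, Protocol 9.4.1.** "Baseline is defined as last available value prior to first dose of IMP". SAP 6.1.2 agrees.
- **Protocol 8.10.1** defines the rise "for seropositive pre-immunization sera: a titer which is 4-fold higher than the measured pre-immunization titer" and does not say which dose it means.
- **Tables, SAP 6.1.1.** Results are shown for the "Group B immunology subset by transplant status, and total". The same section defines the paired statistic: "Geometric mean fold rise (GMFR) is calculated as the mean of the difference of logarithmically transformed assay results".
- **Time points, SAP 1.1.** For transplant subjects the secondary titers are taken after Dose 1 "and at Dose 2 (Day 1) and then Day 8, Weeks 4, 12 and, 26 post Dose 2". Protocol Table 2a places the Visit 8 draw before injection 2.
- **Blood and duration.** Protocol 8.11 gives about 620 mL for the Immunology Subgroup of Group B, which includes the transplant subjects. Protocol 1.1 and SAP 1.2 give about 30 weeks per subject.

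**The concern.** The protocol wants evidence on the fourth vaccination in transplant recipients (Sections 1.1, 2.2 and 4.2). Section 2.2 reports that responses after the third vaccination varied widely between subjects. It cites a published series in which a fourth dose raised responses in people who had responded poorly or not at all. Whether Dose 2 lifts those same subjects is a within-subject question.

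The planned reference cannot answer it. At Visits 9 to 12 the fold rise mixes what remains of the Dose 1 response with whatever Dose 2 adds, and seroconversion against the parent-trial baseline also includes the parent-trial doses. A reader could take seroconversion after Dose 2 as an effect of Dose 2 when it was already present at Visit 8.

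The per-visit denominators add to this. Receipt of a non-trial vaccine is a reason to discontinue a transplant subject (Protocol 7.2), and later data are excluded (SAP 6.1), so different subjects may contribute at Visit 8 and at later visits.

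**Working it through.** **1. Identity.** For visit k after Dose 2, Vk/V1 = (V8/V1) × (Vk/V8). The plan reports the left side; the Dose 2 change is the last factor. With R = V8/V1, the Dose 2 fold needed to be counted as seroconverted is 4/R:

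| R at Visit 8 | 1 | 2 | 4 | 8 |
|---|---|---|---|---|
| Dose 2 fold needed | 4 | 2 | 1 | 0.5 |

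Example with hypothetical titers at Visits 1, 8 and 10 of 10, 80 and 45: the planned fold rise is 45/10 = 4.5, so the subject is seroconverted, while the titer fell to 45/80 = 0.56 of its Visit 8 value.

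**2. Can the per-visit tables stand in?** The documents give no Visit 8 titers, so this is an illustration. Assume n = 15 (the planned ceiling), the same Visit 1 titer in all, Visit 8 folds of 1, 4 and 16 (five subjects each), and Visit 9 folds of 4, 16 and 64 (five each). Confidence intervals for geometric means use the t-distribution on log10, as in SAP 6.1.1.

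- Visit 8: mean log10 = 0.602, SD = 0.602 × √(10/14) = 0.509, half-width = 2.145 × 0.509/√15 = 0.282. The GMFR is 4.0 (95% CI 2.1 to 7.7), with 10/15 seroconverted.
- Visit 9: the same SD. The GMFR is 16.0 (8.4 to 30.6), with 15/15 seroconverted.

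Two pairings of subjects give exactly these rows:

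| | Paired GMFR, Visit 9 to Visit 8 | 4-fold rise from Visit 8 (exact 95% CI) |
|---|---|---|
| A: every subject rises 4-fold | 4.0 (no spread) | 15/15 (78 to 100%) |
| B: 1→64, 4→4, 16→16 | 4.0 (1.3 to 12.3) | 5/15 (12 to 62%) |

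The point estimate, 16.0/4.0 = 4.0, can be recovered from the planned tables when the same subjects contribute at both visits. The interval and the count cannot.

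**3. Changing denominators.** Start from 10/15 (67%) at Visit 8. If 0, 3 or 5 subjects who had not seroconverted leave, the later rate is 10/15 (67%), 10/12 (83%) or 10/10 (100%) with no change in any titer.

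**4. Separate item: blood volume.** Count the marked draws in each schedule, leaving out early termination. The stated figures reproduce exactly:

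- Table 1: 4×15 + 5×15 + 4×120 = 615 mL.
- Table 2: 15 + 7×15 + 5×100 = 620 mL.
- Table 3: 15 + 7×15 = 120 mL.
- Early maximum, Table 2 Visits 0 to 5: 15 + 5×15 + 3×100 = 390 mL.

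So 620 mL is Table 2 alone. For a transplant subject given Dose 2:

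- Table 2, consent at Visit 6 (Visit 7 skipped, no CMI draw at consent): 15 + 6×15 + 3×100 = 405 mL.
- Table 2, consent at Visit 7: 15 + 7×15 + 4×100 = 520 mL.
- Table 2a: 3×3 + 5×15 + 5×100 = 584 mL.
- Totals: 989 or 1,104 mL, which is 1.60 or 1.78 times 620.
- If footnote h of Table 2 removes the Visit 4 CMI draw: 889 or 1,004 mL (1.43 or 1.62 times).

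Visits 8 to 10 take 3 × 118 = 354 mL, or 369 mL with the consent visit, which is below the 450 mL per 28 days in Protocol 2.3.1. The 390 mL early maximum is also unaffected.

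**5. Separate item: duration.** The stated figure is 4 + 26 = 30 weeks. With Dose 2 at 3 months (13.0 weeks) or 7 months (30.4 weeks): 4 + 13.0 + 26 = 43.0 weeks, to 4 + 30.4 + 26 = 60.4 weeks.

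**The case against.** The strongest reply is that nothing stated is left undone. The secondary objective is change from baseline, the protocol defines baseline as the value before the first dose, and the SAP reports that at every visit by transplant status. The trial is descriptive, and the SAP nowhere says that seroconversion at Visit 9 is due to Dose 2. The Visit 8 row sits beside it, GMTs and ranges show level and spread, and with at most 15 subjects the count can be read from the listings. The exploratory time-course objective covers the same post-Dose-2 samples and may be analyzed elsewhere. The illustration uses constructed extremes.

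Much of this stands. The SAP does not contradict the protocol, and Protocol 8.10.1 allows a Visit 8 reference without requiring one. The pairings are extreme: A has no spread, and B has a log-scale correlation of −0.5 between visits. They show what the tables leave open, not what is likely. The identical-tables statement covers results against this trial's baseline; parent-baseline seroconversion also depends on titers that the example does not set.

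It does not remove the gap. A listing is not a planned summary, and with so few subjects a reference chosen after seeing the data is open to question. SAP 6.7 says only that another document may describe the exploratory work. For adverse events, SAP 6.4.3 already gives transplant subjects an interval that starts at the second injection; immunogenicity has no counterpart.

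The blood and duration figures are protocol text, not an analysis choice, and carry no weight for the main point.

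**Conclusion.** The concern holds. It is a gap between the stated interest in the fourth vaccination and the planned summaries, and it should be closed before analysis. Missing are the paired interval and the number of subjects with a 4-fold rise from Visit 8; the paired point estimate is also lost when the contributing subjects differ between visits. It affects at most 15 subjects. How far the cumulative results would differ from the Dose 2 change depends on Visit 8 titers that the documents do not give, so the 15/15 against 5/15 contrast shows possible ambiguity and is not a forecast.

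The separate item rests on counting draws and weeks in the protocol's own tables. About 620 mL and about 30 weeks are right for subjects followed under Table 2 only, and too low for transplant subjects given Dose 2. The volume range depends on the consent visit and on how footnote h is read.

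**What to change.** **SAP 6.5.2 and 6.5.3.** For transplant subjects who receive Dose 2, add at Visits 9 to 12, in subjects with both values:

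- the paired GMFR with 95% CI against the Visit 8 pre-dose titer, by the method already in SAP 6.1.1;
- the number and percentage with at least a 4-fold rise from Visit 8, with exact 95% CI and the paired denominator shown.

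Keep the Visit 1 and parent-baseline results and label them cumulative. The cost is a definition line and a few table rows, with no new samples.

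**Protocol, separately.** For transplant subjects given Dose 2, restate Section 8.11 as about 990 to 1,105 mL, or about 890 to 1,005 mL if footnote h is meant to remove the Visit 4 CMI draw. Say which is meant, since the exploratory CMI endpoint in Section 3 lists a Week 4 sample. Reconcile the 30-week duration in Protocol 1.1 and SAP 1.2 with Tables 2 and 2a. The cost is restated text only.

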6.5.3. Seroconversion

Definition

Seroconversion is defined as a minimum of 4-fold rise of antibody titers as compared to

- parent trial (BNT162-01 or BNT162-04) baseline (only for titers derived from reference strain;baseline refers to pre-dose V1 in BNT162-01 or pre-dose V1 in BNT162-04)
- BNT162-14 baseline, i.e., the last value prior to first injection of IMP (Dose 1) given in this BNT162-14 trial on Day 1, including unscheduled visits (for both titers derived from reference strain and from SARS-CoV-2 variant B.1.351)

Analysis

The number of subjects with seroconversion in antibody titers (ELISA) derived from reference will be summarized by number and percentage with 95% confidence interval for all post-baseline time points for Group A, Group B and the immunology subset. The denominator of the percentages will be the number of subjects with data available at the respective visit.

The analysis based on BNT162-14 baseline, will be performed for antibody titers (ELISA) derived from SARS-CoV-2 variant B.1.351 for Group A only.

Seroconversion data of the antibody titer (ELISA) will be listed.

The same analysis will be repeated for neutralizing antibody titers

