6.1.2. Definitions and derivations

Unscheduled visits

Unscheduled visits will not be included in the summary tables but will be included in the listings.

Variables

Unless otherwise specified, **baseline** is defined as last value prior to first injection of IMP (Dose 1) given in this BNT162-14 trial on Day 1, including unscheduled visits.

Change from baseline will be calculated as follows:

• Change from baseline = post-baseline assessment value – baseline assessment value.

Duration [days] will be calculated as follows:

• Duration [days] = last observation date – first observation date + 1

Time from first injection (Dose 1) to first reaction will be calculated as follows: Time from first injection to first reaction [days] = first reaction date – date of first injection (Dose 1) + 1

Time from first reaction to last reaction will be calculated as follows:

Time from first to last reaction [days] = last reaction date – first reaction date + 1

Days since last injection will be calculated as follows:

Days since last injection = onset date of AE – date of last injection +1

For conversion of days to months or years the following rules will be applied:

- 1 month = 30.25 days
- 1 year = 365.25 days

Study Day and are defined as follows:

- Study day:
 - If study date < date of first injection (Dose 1), then study day = study date date of first injection
 - If study date >= date of first injection (Dose 1), then study day = study date date of first injection + 1

Fold rise will be calculated as follows:

• Fold rise = post-dose value / baseline value

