6.1.3. Missing data

As a general rule, missing data will not be imputed (i.e., missing data will not be replaced but will be handled as "missing" in the statistical evaluation), with the following exceptions for summary analyses:

Clinical safety laboratory variables given as "<xx" will be evaluated as 0.5*xx in the summary tables. In the listings they will be displayed as "<xx" or similar.

Data values below lower limit of quantification (LLOQ) or detection (LLOD) will be imputed with 0.5*LLOQ or 0.5*LLOD, respectively, for the analysis of continuous data. Values above the upper limit of quantification (ULOQ) or detection (ULOD) will be imputed with 2*ULOQ or 2*ULOD, respectively, for the analysis of continuous data. In the listings they will be displayed as "<xx" or ">yy" as appropriate. In the tables they will be displayed as "<LLOQ"/("<LLOD" or ">ULOQ"/(">ULOD" in descriptive statistics (e.g., in mean, median, min, max) as appropriate. A footnote will be added to show the value of LLOQ or LLOD or ULOQ or ULOD.

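### For neutralizing titers, SAP 6.5.3 drops the protocol's seronegative branch of the seroconversion rule without declaring it, so the cut-off for a baseline below LOD is unstated and may be half the protocol's

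*SAP*

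**What the plan says.** **Protocol 8.10.1** treats the two assay types separately. For the functional titer it fixes serostatus first: "Seronegative is defined as titers below the starting dilution (i.e., below the limit of detection of the assay"). It then gives two branches. The first reads "for seronegative pre-immunization sera: a titer ≥ 4-times the limit of detection". The second, for sera already positive, requires "a titer which is 4-fold higher than the measured pre-immunization titer". For the binding assay it gives only a plain 4-fold increase, with no LOD branch.

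**SAP 6.5.3** has its own definition: "Seroconversion is defined as a minimum of 4-fold rise of antibody titers as compared to" one of two baselines. One is the BNT162-14 baseline. The other, used for reference-strain titers only, is the parent-trial baseline, where "baseline refers to pre-dose V1 in BNT162-01 or pre-dose V1 in BNT162-04". The analysis is written out for ELISA and ends: "The same analysis will be repeated for neutralizing antibody titers". There is no split by serostatus and no reference to protocol 8.10.1.

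**SAP 6.1.2** sets "Fold rise = post-dose value / baseline value". **SAP 6.1.3** says that values under an assay limit "will be imputed with 0.5*LLOQ or 0.5*LLOD, respectively, for the analysis of continuous data". The SAP introduction says that changes from the protocol are recorded in Appendix 1. That appendix (SAP 7.1) has one entry, on the grading shown in the overall AE table.

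**The concern.** The protocol's LOD branch exists only for the neutralizing assay. The SAP writes its rule for ELISA, where no such branch is needed, and carries it over to neutralization, where one is. A table labelled as neutralizing seroconversion would then use a definition other than the protocol's, with no entry in the place where the SAP says such changes are recorded.

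The subjects at issue are those with no detectable neutralizing titer at the baseline used and only a low titer afterwards. The question is whether such weak responders count as seroconverters. It bears most on the transplant subjects. Protocol 2.2 describes their neutralizing responses as poor and mentions low, negative or inconsistent responders, and SAP 6.1.1 plans tables by transplant status.

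**Working it through.** No rate is stated in the plan, so the check compares cut-offs. Titers are in units of LOD, and the SAP's LLOD is taken to be the protocol's LOD.

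**Inputs**
- Protocol cut-off, baseline below LOD: 4 (protocol 8.10.1).
- Protocol cut-off, measured baseline b ≥ 1: 4b (protocol 8.10.1).
- SAP rule: post / baseline ≥ 4 (SAP 6.5.3 and 6.1.2). SAP 6.1.2 and 6.5.2 define fold rise against the BNT162-14 baseline; I use the same ratio for the parent-trial baseline.
- SAP value for a result below LLOD: 0.5 (SAP 6.1.3).
- Response per time point: geometric mean of two replicates (SAP 6.5.1).

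**Seropositive baseline.** Both rules give 4b. They agree.

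**Baseline below LOD, imputation feeds the flag.** SAP cut-off = 4 x 0.5 = 2. Protocol cut-off = 4. Ratio = 2 / 4 = 0.5.

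| Post titer (x LOD) | Post / 0.5 | SAP flag | Protocol flag |
|---|---|---|---|
| 1.99 | 3.98 | no | no |
| 2 | 4 | yes | no |
| 3.99 | 7.98 | yes | no |
| 4 | 8 | yes | yes |

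The rules disagree for post titers from 2 to just under 4. Every subject who reaches 4 also reaches 2, so on this reading the SAP rate can only equal or exceed the protocol rate.

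**One replicate below LOD, the other at LOD.** Geometric mean = √(0.5 x 1) = 0.71, still below LOD. SAP cut-off = 4 x 0.71 = 2.83; protocol cut-off = 4. The direction is the same and the band narrower.

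**Baseline below LOD, no imputation for the flag.** The ratio has no denominator, so the flag is undefined. SAP 6.5.3 bases percentages on subjects with data at the visit. It does not say whether such a subject counts as a non-converter or is left out.

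**Imputation at 0.5*LLOQ.** SAP cut-off = 4 x 0.5 x LLOQ = 2x LLOQ. This equals 4x LOD only if LLOQ = 2x LLOD. It is lower if the LLOQ is nearer the LOD (LLOQ = 1.5: cut-off 3) and higher if further away (LLOQ = 3: cut-off 6). The documents give no LLOQ for this assay.

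**Size in the transplant subgroup.** SAP 1.2 allows up to 15. One reclassified subject moves the rate by 1/15 = 6.7 points, and by more if fewer than 15 have data at the visit.

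**The case against.** **The imputation may not reach the flag.** SAP 6.1.3 confines it to continuous data, and seroconversion is a yes/no result. This stands: a reader might infer that the SAP fixes the cut-off at 2x LOD, and the text does not say so. But fold rise is itself summarized as a continuous variable in SAP 6.5.2, so applying a threshold of 4 to that derived variable is the obvious programming route. The alternative leaves the flag undefined. Neither route yields the protocol rule.

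**The SAP only restates the protocol's lead sentence.** Protocol 8.10.1 opens with a 4-fold increase, and the SAP agrees with that and with the seropositive branch. This is true, but the protocol goes on to say what the increase means for a seronegative serum. The SAP sets its own definition without pointing back, although it cites protocol sections elsewhere (SAP 6.4.1 and 6.4.3).

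**The parent-trial comparison is the SAP's own.** Protocol 9.4.1 takes baseline as the last value before the first dose of IMP, and 8.10.1 does not tie its pre-immunization serum to the parent trial. This stands: for that comparison, departure from a protocol-defined rate is less clear. It is still sensible to use one rule at both baselines.

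**The consequence is small.** No hypothesis is tested, and seroconversion is not among the named endpoints. Antibody responses and seroconversion data will be listed, with values under the limit shown as such, so the protocol rate could be rebuilt from the listings. All of this limits the weight of the point. It does not make the table match the protocol.

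**Conclusion.** The point holds as an undeclared departure from the protocol, confined to neutralizing titers with a baseline below LOD. The omission of the branch and the silence of Appendix 1 are certain from the text. The 2x LOD cut-off is conditional: it assumes that 0.5*LLOD imputation feeds the flag and that both replicates are below LOD.

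On that reading, the subjects who change status have a baseline below LOD and a post titer from 2x to under 4x LOD. A reader might go on to infer a particular inflation of the rate. The documents do not support one, because they report neither titers in LOD units nor the number seronegative at either baseline. At the BNT162-14 baseline all subjects have already had one or two BNT162 doses, so fewer should be affected than at the parent-trial baseline. That is an expectation and not a documented count. For transplant subjects, protocol 2.2 mentions weak responders but also reports up to 70% at the level it calls protective; neither statement converts to LOD units. All that can be said is that one reclassified subject there is worth at least 6.7 points.

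Nor should the point be read as touching the main immunogenicity summaries: GMT, GMFR and the ELISA rule are unaffected.

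**What to change.** In SAP 6.5.3, for neutralizing titers:
- If the baseline is below LOD, require a post titer of at least 4x LOD; otherwise require at least 4x the measured baseline.
- State that baselines imputed at half a limit do not feed this flag.
- Apply the rule to both the BNT162-14 and the parent-trial baseline.

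Keep the plain 4-fold rule for ELISA, and keep the imputation for GMT and GMFR. If the single rule is intended for neutralizing titers, enter it in Appendix 1 with the cut-off it implies for a baseline below LOD.

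The cost is a few lines of text and one derivation, with no new data. The reported neutralizing seroconversion rate may be lower than under the current text, by an amount that depends on how many subjects are seronegative at the baseline used.
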